This is an open-label extension study to roll-over eligible subjects from Eisai sponsored lenvatinib studies. The subject can be enrolled in the roll-over study for the purpose of long-term safety data collection. The subjects may roll-over no sooner than the primary completion dates in their parent study or after all study data for primary outcome measure were collected for the parent study. The parent study is defined as the Eisai-sponsored lenvatinib clinical study in which the subject was receiving lenvatinib either as monotherapy or as combination therapy or was receiving any other comparator therapy. The subjects willing to participate in the roll-over study have to sign the ICF for Study E7080-G000-604. The "End of Treatment" assessments in the parent study are to be completed and reviewed by the investigator prior to enrollment of the subject into Study E7080-G000-604. Eligibility for the roll-over study is to be established based on meeting all inclusion and exclusion criteria for Study E7080-G000-604. The intention is that the subject will not be without study drug during transition from the parent study to the roll-over study. The subjects in Study E7080-G000-604 should receive the first dose of the study drug the following day after the last dose of the study drug in the parent study. All treatment emergent adverse events (TEAEs) and serious adverse events (SAEs), regardless of relationship to study drug or procedure, should be recorded beginning from the time the subject signs the roll-over study ICF for up to 28 days after the last dose of study drug(s) (or $5 \times$ halflife of the study drug[s], whichever is longer).

Treatment Cohorts:

After signing the consent form for the study and meeting all inclusion and exclusion criteria, subjects will be assigned to a treatment cohort as described below to continue treatment with study drug(s) in the study protocol.

Cohorts	Interventions
Cohort A Subjects who received lenvatinib monotherapy or who crossed over from a comparator arm to receive lenvatinib monotherapy in their parent study will continue to receive lenvatinib monotherapy	Lenvatinib
Cohort B Subjects who received lenvatinib combination therapy or who crossed over from a comparator arm to receive lenvatinib combination therapy in their parent study will continue to receive lenvatinib combination therapy	Lenvatinib combination therapy

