The other assessments including vital signs, physical examinations, ECG, and clinical laboratory assessments should be performed as per local standard of care and as per discretion of the investigator. For urgent safety issues, all appropriate medical care is to be administered to the subject and the appropriate study team member listed in the Investigator Study File should be contacted. All TEAEs and SAEs, regardless of relationship to study drug or procedure, should be recorded beginning from the time the subject signs the roll-over study ICF for up to 28 days after last dose of study drug(s) (or $5 \times half$ -life of the study drug[s], whichever is longer). Any exposure to study drug(s) through breastfeeding during the roll-over study or within 120 days of the last study drug(s), or 30 days following the last study drug(s) if the subject initiates a new anticancer therapy, whichever occurs first, must be reported. SAE management and reporting requirements specific to study drugs will be addressed as per instructions in the parent study protocol.

Number of Subjects

It is expected that approximately 50 subjects will be initially rolled over into the study. It is anticipated that additional subjects may also roll over into the study in the future.

Inclusion Criteria

It is required for all subjects currently participating in other lenvatinib studies to meet the following eligibility criteria.

- 1. Provide signed written informed consent for the roll-over study
- 2. Currently enrolled in an Eisai sponsored lenvatinib clinical study and still receiving at least one of the study drugs from that protocol
- 3. Currently deriving clinical benefit from at least one of the study drug(s) as determined by the investigator
- 4. Must be able and willing to comply with the current roll-over protocol requirements
- 5. Continued ability to swallow and retain orally administered study drug(s)
- 6. Does not have any clinically significant gastrointestinal abnormalities that may alter absorption such as malabsorption syndrome or major resection of the stomach or bowels
- 7. Women of childbearing potential and men with reproductive potential (if specified by the parent study) must be willing to continue to use highly effective methods of contraception as per local practices of standard of care during the period of the study

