9 INVESTIGATIONAL PLAN

9.1 Overall Study Design and Plan

This is an open-label extension study to roll-over eligible subjects from Eisai sponsored lenvatinib studies. The subject can be enrolled in the roll-over study for the purpose of long-term safety data collection. The transition would occur after the completion and evaluation of the primary endpoint of the parent studies or after all study data for the primary outcome measure were evaluated for the parent study. The parent study is defined as the Eisai-sponsored lenvatinib clinical study in which the subject was receiving lenvatinib either as monotherapy or as combination therapy, or was receiving any other comparator therapy. The subjects willing to participate in the roll-over study have to sign the ICF for Study E7080-G000-604. The "End of Treatment" assessments in the parent study are to be completed and reviewed by the investigator prior to subject enrollment into Study E7080-G000-604. The eligibility for the roll-over study is to be established based on meeting all inclusion and exclusion criteria described in Section 9.3. The intention is that the subject will not be without study drug during transition from the parent study to the roll-over study. The subjects in Study E7080-G000-604 should receive the first dose of the study drug the following day after the last dose of the study drug in the parent study. All TEAEs and SAEs, regardless of relationship to study drug or procedure, should be recorded beginning from the time the subject signs the roll-over study ICF for up to 28 days after last dose of study drug(s) (or 5 × half-life of study drug[s], whichever is longer). SAE management and reporting requirements specific to study drugs will be addressed as per the instructions in the parent study protocol. Ongoing AEs in the parent study will remain ongoing at the time of discontinuation in the parent study, and the roll-over study will only capture new or worsening TEAEs occurring after signing the roll-over study ICF.

Figure 1 Study Design for Study E7080-G000-604

Screening period: From approximately Day -30 to Day -1, subjects may remain on the parent study.

Cohort A: Subjects who received lenvatinib monotherapy or who crossed over from a comparator arm to receive lenvatinib monotherapy in their parent study will continue to receive lenvatinib monotherapy

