9.5.7.1 Adverse Events

An adverse event (AE) is any untoward medical occurrence in a patient or clinical investigation subject administered an investigational product. An AE does not necessarily have a causal relationship with the medicinal product. For this study, the study drug(s) is/are lenvatinib, or lenvatinib combination regimen, or any other comparator therapy (except placebo) as per the parent study.

AEs collected in this study must be treatment-emergent adverse events (TEAE). This is defined as an AE that emerges during treatment in the roll-over study, having been absent before the time the subject signs the roll-over study ICF or

- Re-emerges during treatment in the roll-over study, having been present before signing the ICF but stopped before signing the ICF, or
- Worsens in severity during treatment in the roll-over study relative to the pre-ICF state, when the AE is continuous.

The criteria for identifying TEAEs in this study are:

- Any unfavorable and unintended sign (including an abnormal laboratory finding), symptom, or disease temporally associated with the use of an investigational product, whether or not considered related to the investigational product
- Any new disease or exacerbation of an existing disease.

- Any deterioration in nonprotocol-required measurements of a laboratory value or other clinical test (eg, ECG or x-ray) that results in symptoms, a change in treatment, or discontinuation of study drug
- Recurrence of an intermittent medical condition (eg, headache) not present pretreatment (Baseline)
- An abnormal laboratory test result should be considered a TEAE if the identified laboratory abnormality leads to any type of intervention, withdrawal of study drug, or withholding of study drug, whether prescribed in the protocol or not

A laboratory result should be considered by the investigator to be a TEAE if it:

- Results in the withdrawal of study drug
- Results in withholding of study drug pending some investigational outcome
- Results in an intervention, based on medical evaluation (eg, potassium supplement for hypokalemia
- Results in any out-of-range laboratory value that in the investigator's judgment fulfills the definitions of a TEAE with regard to the subject's medical profile

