4.2 Overall Study Design and Plan

This is an open-label extension study to roll over eligible subjects from Eisai-sponsored lenvatinib studies. Subjects are enrolled in the rollover study for the purpose of long-term safety data collection. The transition from the parent study to the extension study would occur after the completion and evaluation of the primary endpoint of the parent studies or after all study data for the primary outcome measure were evaluated for the parent study. The parent study is defined as the Eisai-sponsored lenvatinib clinical study in which the subject was receiving lenvatinib either as monotherapy or as combination therapy, or was receiving any other comparator therapy.

The subjects willing to participate in the rollover study have to sign the informed consent form (ICF) for Study E7080-G000-604. The “End-of-Treatment” assessments in the parent study are to be completed and reviewed by the investigator prior to subject enrollment into Study E7080-G000-604. The eligibility for the rollover study is to be established based on meeting all inclusion and exclusion criteria described in Section 9.3 of the protocol. The intention is that the subject will not be without study drug during the transition from the parent study to the rollover study. The subjects in Study E7080-G000-604 should receive the first dose of the study drug the following day after the last dose of the study drug in the parent study. All treatment-emergent adverse events (TEAEs) and serious adverse events (SAEs), regardless of relationship to study drug or procedure, should be recorded beginning from the time the subject signs the rollover study ICF for up to 28 days after the last dose of study drug(s) (or $5 \times$ half-life of study drug[s], whichever is longer). SAE management and reporting requirements specific to study drugs will be addressed as per the instructions in the parent study protocol. Ongoing AEs in the parent study will remain ongoing at the time of discontinuation in the parent study, and the rollover study will capture only new or worsening TEAEs occurring after signing the rollover study ICF.

Screening period:

From approximately Day -30 to Day -1, subjects may remain on the parent study.

Subjects will be enrolled into the study under the following cohort definitions.

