6.5.2 Adverse Events

The adverse event (AE) verbatim descriptions (investigator terms from the eCRF) will be classified into standardized medical terminology using the Medical Dictionary for Regulatory

Activities (MedDRA). The linked MedDRA preferred term (PT) and primary system organ class (SOC) are also captured in the database.

AEs collected in this study must be treatment-emergent adverse events (TEAE). This is defined as an AE that emerges during treatment in the rollover study, having been absent before the time the subject signs the rollover study ICF or

- Re-emerges during treatment in the rollover study, having been present before signing the ICF but stopped before signing the ICF, or
- Worsens in severity during treatment in the rollover study relative to the pre-ICF state, when the AE is continuous.

Only those AEs that are treatment emergent will be included in summary tables. TEAEs are those occurring on or after the first dose date of study drug and on or before 28 days after the last dose of study drug. All TEAEs will be presented in subject data listings.

An overview table, including the number and percentage of subjects with TEAEs, SAEs, deaths, and those with TEAEs that led to study drug discontinuation, interruption, or dose reduction will be provided. The number (percentage) of subjects with TEAEs will be summarized by SOC and PT, by relationship to study drug (Yes [related] and No [not related]), and by CTCAE toxicity grade as follows:

- Overview of TEAEs
- TEAEs by SOC and PT
- TEAEs by decreasing frequency of PT
- TEAEs with CTCAE Grade ≥ 3 by decreasing incidence of PT
- Treatment-emergent serious AEs by decreasing incidence of PT
- Overview of treatment-related TEAEs
- Treatment-related TEAEs by SOC and PT
- Treatment-related TEAEs by decreasing frequency of PT
- Treatment-related TEAEs with CTCAE Grade ≥ 3 by decreasing incidence of PT
- Treatment-related treatment-emergent serious AEs by decreasing incidence of PT
- Fatal TEAEs by decreasing incidence of PT
- TEAEs leading to treatment discontinuation of lenvatinib

The following listings will be provided for the subjects in the Safety Analysis Set:

- Demographics

- Disposition
- Lenvatinib dosing
- All AEs
- All SAEs
- Adverse events with CTCAE Grade 3 or above
- All AEs leading to study drug discontinuation
- All fatal AEs

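### SAP 6.5.2 closes the treatment-emergent window at 28 days, but SAP 4.2 and the protocol record TEAEs and SAEs for longer when a study drug's half-life exceeds 5.6 days

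*SAP*

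**What the plan says.** Two current rules set how long after the last dose an event counts.

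- **Recording.** Protocol 9.1 has TEAEs and SAEs recorded from consent "for up to 28 days after last dose of study drug(s) (or 5 × half-life of study drug[s], whichever is longer". The synopsis (study design and safety assessments) and Protocol 9.5.7.1 repeat this. SAP 4.2 adopts it, with the same extension: "half-life of study drug[s], whichever is longer".
- **Tabulation.** SAP 6.5.2 ends the treatment-emergent period "on or before 28 days after the last dose of study drug", with no half-life extension. It adds: "Only those AEs that are treatment emergent will be included in summary tables".

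The same SAP section also states: "AEs collected in this study must be treatment-emergent adverse events (TEAE". The protocol's TEAE definition (9.5.7.1 and 9.7.1.8) refers to treatment in the roll-over study and gives no closing day.

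Study drugs go beyond lenvatinib. Protocol 9.5.7.1 says "the study drug(s) is/are lenvatinib, or lenvatinib combination regimen, or any other comparator therapy (except placebo". Cohorts B and C exist for combination and comparator subjects.

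**The concern.** The SAP uses one term, TEAE, with two different end points. An event that occurs after day 28 but within five half-lives of a long-lived drug is recorded as a TEAE under Section 4.2, yet it is not a TEAE under Section 6.5.2. SAP 6.5.3 widens the difficulty. It refers to Protocol 9.5.7.1 for the TEAE definition of laboratory abnormalities and says that these will be summarised with the other TEAEs. A late one would not be.

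Long-term safety is the only objective and no efficacy analysis is planned, so the TEAE tables are the main output. A window shorter than the recording period can lower the number of subjects counted with an event and can never raise it. The serious, Grade ≥3, related and fatal tables matter most here. A late event of that kind would appear in a listing, but someone reading only the tables would not see it.

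**Working it through.** **Inputs**

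- Tabulation limit: 28 days after last dose (SAP 6.5.2).
- Recording limit: the longer of 28 days and 5 × half-life (SAP 4.2; Protocol synopsis, 9.1 and 9.5.7.1).
- Lenvatinib: five half-lives equated with one week (Protocol 9.4.1.4, surgery guidance).
- Other study drugs: no half-life is given. Protocol 7 and 9.4.1.5 name a monoclonal antibody, pembrolizumab, in combination with lenvatinib.
- Study period: ends 30 days after the last subject's last dose (synopsis).

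The plan gives no figure of its own to reproduce on this point.

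**1. When the rules differ.** They differ if 5 × t½ > 28 days, that is, t½ > 28/5 = 5.6 days.

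**2. Lenvatinib.** 5 × t½ is about 7 days, so t½ is about 7/5 = 1.4 days. The recording limit is max(28, 7) = 28 days, the same as the tabulation limit. The gap is 0.

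**3. Other drugs.** Gap = max(28, 5 × t½) − 28 days. The half-lives above 5.6 days in this table are assumptions for illustration and come from neither document.

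| Assumed t½ (days) | 5 × t½ | Recording limit | Recorded but not tabulated |
|---|---|---|---|
| 5.6 | 28 | 28 | 0 days |
| 7 | 35 | 35 | 7 days |
| 14 | 70 | 70 | 42 days |
| 25 | 125 | 125 | 97 days |

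These are lengths of time. They do not say how many events or subjects would be affected.

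**4. What happens to one late event.** Take an event after day 28 and within the recording limit. It is recorded under SAP 4.2 and fails the SAP 6.5.2 limit, so it is excluded from the summary tables. It still appears in the all-AE listing and, where it qualifies, in the SAE, Grade 3 or above and fatal-AE listings. It misses only the tables it would have qualified for. For a non-serious, unrelated Grade 1 event, these are the overview, the SOC/PT table and the table by PT frequency. A serious, related or fatal event would miss more. The tables count subjects, so a subject who already had the same preferred term inside the window keeps that row.

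**5. Study period.** 5 × t½ exceeds 30 days when t½ > 30/5 = 6 days. For the last subject on such a drug, the recording rule runs past the stated end of the study period. The synopsis therefore does not fit fully with its own recording rule.

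**The case against.** The strongest reply is that a recording period and an analysis window are different things, and that the second may properly be shorter. The protocol sets no closing day for treatment emergence, and Protocol 9.7.1 leaves analytical detail to the SAP. Taken literally, the protocol's definition stops with treatment, so 28 days is the more generous reading. The limit also looks deliberate, since the SAP version history lists it as a clarification in version 2.0. A fixed window keeps the tables uniform when Protocol 9.5.9.1 refers SAE collection to the various parent protocols and the study period closes at 30 days.

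Much of this stands. A 28-day analysis window is defensible in itself. A reader might infer that it was brought in without notice. The documents do not support that: the version history states it, and Protocol 9.7.5 sends SAP revisions to the clinical study report.

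The reply still does not reconcile the text. SAP 4.2 calls the events recorded to the longer limit TEAEs, and SAP 6.5.2 says that collected events must be TEAEs, then denies that status to some of them. The SAP nowhere says that its analysis window is meant to be shorter than its recording window, and it gives no reason.

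**Conclusion.** The conflict in the wording is certain. Its practical effect is unproven and may be nil. It is zero for lenvatinib and arises only for a partner or comparator with a half-life above 5.6 days.

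A reader might infer that this trial's safety tables are understated. The documents do not support that. They give no half-life for any other drug and do not show that any enrolled subject took a long-lived one. The antibody appears in the background and interaction sections, and the only comparator named in Protocol 9.4.1 is sorafenib, for China. A reader might also infer that a late event disappears from nearly every table. It is lost only from those it qualifies for, it remains listed, and subject-level counting softens the loss further.

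The remaining finding is narrow. If a long-lived study drug was taken, any distortion is one-sided, towards fewer subjects counted with events, on the study's only objective. That justifies a correction that costs almost nothing. It does not cast doubt on the analysis as a whole.

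**What to change.** Amend SAP 6.5.2 in one of two ways.

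**(a) Align the windows.** For each study drug the subject received in the roll-over study, compute that drug's own last dose + max(28 days, 5 × its half-life). End the subject's window at the latest of these dates. Each half-life must be tied to its own drug's last dose. Applying the longest half-life to the last dose of any drug would over-extend the window for a subject who stopped a long-lived partner early and continued lenvatinib.

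**(b) Keep 28 days as the main window.** State that it is shorter than the recording period in SAP 4.2, and add a summary row for TEAEs, SAEs and fatal events recorded after day 28.

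Under either option, add a footnote that late collection may be uneven, because SAE collection is referred to the parent protocols and the study period ends 30 days after the last subject's last dose. That end date should be reconciled with the five half-lives recording rule.

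Option (a) costs one sentence and a half-life look-up per drug in the ADaM specification. Option (b) costs one sentence and one table row. Counts may rise slightly. If no study drug has a half-life above 5.6 days, the tables do not change, and a sentence saying so closes the point.

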The efficacy and safety of lenvatinib treatment has also been evaluated in the multicenter. randomized, double-blind, placebo-controlled Phase 3 trial E7080-G000-303 (SELECT trial) in patients with RR-DTC with documented disease progression within 13 months. Patients were stratified by age (≤ 65 , > 65 years), region and ≤ 1 prior VEGFR-targeted therapies and randomized 2:1 to lenvatinib or placebo arms (24 mg a day, 28-day cycle). The primary endpoint was PFS assessed by Independent Radiologic Review; the secondary endpoints included ORR (ie, complete response [CR] + partial response [PR]), OS, and safety. A total of 392 patients (63.0 years median age; 51.0% male) were randomized at over 100 sites in Europe, North and South America, and Asia. Patients in the lenvatinib arm had a significantly prolonged PFS (hazard ratio = 0.21, 95% confidence interval [CI] = 0.14-0.31; $P \le 0001$) with a median PFS for the lenvatinib arm of 18.3 months (95% CI = 15.1-not evaluable) vs the placebo arm: 3.6 months (95% CI = 2.2–3.7). The lenvatinib arm PFS benefit was observed in all predefined subgroups: median lenvatinib arm PFS for patients with prior vs no prior VEGF-therapy was 15.1 months (n=66) and 18.7 months (n=195). respectively; rates (n) of CRs for the lenvatinib arm vs placebo arm were 1.5% (4) and 0, respectively; PRs for the lenvatinib arm vs the placebo arm were 63.2% (165) and 1.5% (2), respectively. Median exposure durations for the lenvatinib arm vs the placebo arm were 13.8 months and 3.9 months, respectively; median time to lenvatinib response was 2.0 months. Median OS has not been reached; deaths for the lenvatinib arm were 71 (27.2%) and for the placebo arm were 47 (35.9%). The 5 most common lenvatinib treatment-related adverse events (AEs) (any grade) were hypertension (68%), diarrhea (59%), appetite decreased (50%), weight loss (46%), nausea (41%). The most common Grade \geq 3 lenvatinib treatmentrelated AEs (\geq 5%) were hypertension (42%), proteinuria (10%), weight loss (10%), diarrhea (8%), and appetite decreased (5%). The lenvatinib dose was reduced in 78.5% of patients and lenvatinib was discontinued due to AEs in 14.2% of patients (Schlumberger, et al., 2014). Based on the efficacy and safety information to date, patients with RR-DTC may benefit from lenvatinib treatment.

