9.1.1 Treatment Phase

During the Treatment Phase, subjects still on treatment will continue the same treatment they received upon discontinuation of the parent study. Subjects will remain on treatment in consecutive cycles as per the parent study protocol until disease progression, development of unacceptable toxicity, subject request, withdrawal of consent, discontinuation of Study E7080-G000-604 by the sponsor, use of non-permitted concomitant drugs, unacceptable non-compliance with the protocol, or if the subject is lost to follow-up.

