4 INTRODUCTION

The purpose of this statistical analysis plan (SAP) is to describe the procedures and the statistical methods that will be used to analyze and report the results for Eisai Protocol E7080-G000-604. This is a long term, open-label extension study to roll over eligible subjects from Eisai-sponsored lenvatinib studies. This study was conducted in China and several other countries including Australia, Belgium, Germany, Italy, Netherlands, Poland, Romania, South Korea, Thailand, and the United States; summaries will be prepared by region (China vs Rest of World) and across all subjects.

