5 DETERMINATION OF SAMPLE SIZE

This is a rollover open-label safety study; no formal sample size calculations were performed. It is expected that approximately 50 subjects will be initially rolled over to the study. It is anticipated that additional subjects may also roll over to the study in the future. Subjects who meet all of the inclusion criteria and none of the exclusion criteria, with no evidence of progressive disease, and who have tolerated study drug(s) in their parent study without significant toxicities will be rolled over to this study. Subjects with evidence of disease progression but who continue to derive clinical benefit, as determined by the

investigator, would require discussion with the sponsor on an individual case-by-case basis prior to enrollment in this study.

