6.3 Data Analysis General Considerations

Descriptive statistics for continuous variables will include the number of subjects, mean, standard deviation (SD), median, Q1, Q3, and range (minimum, maximum). Categorical variables will be summarized by reporting the number and percentage of subjects. In most cases, the denominator for calculating percentages will be the number of subjects in the column header. Whenever a different subset is used to define the denominator, a footnote will be provided to describe the set of subjects to be used as the denominator. The reporting number of decimal places will be provided in the table shells.

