6.5.1 Extent of Exposure

The length of time on treatment (months), and the quantity of study drug administered [dose intensity (mg/day)] will be summarized.

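### SAP 6.5.2 reports adverse events only as crude percentages with no allowance for time at risk, so pooled and regional incidences cannot be read as long-term risk

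*SAP*

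**What the plan says.** **AE summaries.** SAP 6.5.2 states: "The number (percentage) of subjects with TEAEs will be summarized by SOC and PT". The tables listed there are counts and percentages of subjects, split by relationship, grade, seriousness and outcome. On denominators, SAP 6.3 states: "In most cases, the denominator for calculating percentages will be the number of subjects in the column header". No incidence rate, cumulative incidence or time-to-first-event summary is listed.

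**Columns.** SAP section 4 states that "summaries will be prepared by region (China vs Rest of World) and across all subjects".

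**Time at risk.** Protocol 9.1.1 sets no fixed treatment duration: "Subjects will remain on treatment in consecutive cycles as per the parent study protocol until disease progression", or until another stopping reason such as toxicity, withdrawal or sponsor termination. SAP section 5 leaves entry open: "It is anticipated that additional subjects may also roll over to the study in the future". The analysis window belongs to each subject: "TEAEs are those occurring on or after the first dose date of study drug and on or before 28 days after the last dose" (SAP 6.5.2).

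**Exposure.** SAP 6.5.1 summarises exposure on its own: "The length of time on treatment (months), and the quantity of study drug administered". Nothing links it to the AE counts.

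**Time-related summaries in the protocol.** Protocol 9.7.1.8 plans to summarise the duration of TEAEs and their timing from the start of study medication. Protocol 9.7.1.6 plans time to discontinuation due to a TEAE and time to first dose reduction. The SAP lists none of these, and SAP section 8 expects no change to the planned analyses.

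**The concern.** A percentage of subjects with an event estimates a risk over a definite period only when everyone is observed for about that period. Here the observation period is whatever each subject's course makes it. The pooled percentage is therefore an average over an unstated mix of follow-up times. It is not a one-year risk or a two-year risk, and it cannot be set against another source with a different mix. This holds for the all-subjects column alone, before any question about regions.

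The regional columns add a second, conditional problem. If one region is treated for longer, its percentages will be higher at the same underlying rate. If a region with a higher rate is treated for less time, the percentages can look alike.

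A separate exposure table does not repair this. It gives the overall distribution of time on treatment, but a reader cannot work out from it the person-time to first event for a given grade, seriousness category or preferred term. The time-related summaries that would have helped in part are the ones the SAP leaves out.

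**Working it through.** The plan gives no alpha, power, calculated sample size or follow-up distribution, so it has no figure to reproduce. What follows is an illustration on stated assumptions.

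**From the documents.** AE window from first dose to 28 days after last dose (SAP 6.5.2); about 50 subjects initially (SAP section 5).

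**Assumed.** Time on treatment is exponential with a chosen median M (months). The first-event rate λ per month is constant and the same in both columns. There are 25 subjects per region.

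**Formula.** Let w = 28/30.4375 = 0.92 months and μ = ln 2 / M. Averaging the event probability over the treatment-time distribution gives

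crude % = 1 − exp(−λw) × μ/(μ + λ).

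**Worked case.** λ = 36/1200 = 0.03 per month and M = 12 give μ = 0.0578. Then exp(−0.03 × 0.92) = 0.973, μ/(μ + λ) = 0.658, and crude % = 1 − 0.973 × 0.658 = 36.0%.

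**Step 1: what the pooled percentage means.** At that rate the one-year risk is 1 − exp(−0.36) = 30.2% and the two-year risk is 1 − exp(−0.72) = 51.3%. The crude 36.0% is neither. Under this model the p-th quantile of treatment time is M × log2(1/(1 − p)). With M = 12 the quartiles are 5.0 and 24.0 months, so a wide spread between subjects is plausible under treatment to progression.

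**Step 2: same true rate, different exposure.**

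| Rate per 100 patient-years | M = 6 | M = 12 | M = 18 | M = 24 |
|---|---|---|---|---|
| 12 | 8.8% | 15.5% | 21.3% | 26.4% |
| 36 | 22.8% | 36.0% | 45.3% | 52.3% |
| 120 | 51.1% | 66.6% | 74.6% | 79.6% |

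Reading two columns against each other with no true difference:

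- Equal medians: gap of 0 points.
- 12 versus 18 months: 5.8 to 9.4 points across the three rates.
- 12 versus 24 months: 10.9 to 16.3 points.
- 6 versus 24 months: 17.6 to 29.5 points.

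In a simulation with 25 subjects per region and 20,000 replicates, first events divided by person-time, totalled over replicates, returned the true rate in every case checked (for example 36.0 to 36.1 where the truth was 36).

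**Step 3: masking.** A rate of 48 per 100 patient-years with an 8-month median gives 34.1%. Half that rate, 24, with a 16-month median gives 32.8%. A twofold difference disappears.

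**Step 4: precision.** In the same simulation the chance standard deviation of the difference in crude percentages was about 10 to 14 points. Rates are imprecise too. With 25 subjects, M = 12 and 36 per 100 patient-years, about 25 × 0.360 = 9 first events are expected over 9/0.36 = 25 patient-years. Exact Poisson limits for 9 events are 4.12 and 17.08. Dividing by 25 gives an interval of 16.5 to 68.3 per 100 patient-years around 36.

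**The case against.** **No follow-up data.** A reader might infer that follow-up is very unequal and that the regional percentages mostly reflect how long subjects were followed. The documents do not support that. Neither gives a follow-up distribution, overall or by region, and if exposure is similar the regional distortion is nil. Protocol 9.4.1 has a China-only provision for sorafenib as comparator, while the introduction describes thyroid, renal and liver cancer programmes. A different disease mix is therefore possible, but that is inference.

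**No borrowed magnitude.** It is tempting to take a size from Protocol section 7: "Median exposure durations for the lenvatinib arm vs the placebo arm were 13.8 months and 3.9 months". Those are the two arms of an earlier thyroid cancer trial. Subjects who stayed on placebo in a parent study cannot enrol here, and the contrast says nothing about regions. It should not be used.

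**Descriptive study.** There is no control group, secondary objective, regional test or planned external comparison. Exposure is at least reported. SAP 6.3 allows other denominators with a footnote, and the table shells are a separate document. All of this is true and limits the regional point. It does not give the pooled percentage a time scale, and the SAP text is where a rate should be specified.

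**Burden and small numbers.** SAP version 2.0 deliberately cut the outputs, and with about 50 subjects chance variation can exceed a moderate exposure effect. This is a fair reason to confine the addition to key rows.

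**Rates have limits.** A reader might also infer that exposure-adjusted rates would make China and Rest of World comparable. They would not. The regional columns as described mix monotherapy, combination and comparator cohorts, and a single rate assumes a roughly constant hazard. Counting all events would also need a rule for grade changes, because increases and decreases in grade are both recorded.

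**Conclusion.** The point stands in a limited form. The AE tables specified in SAP 6.5.2 are crude percentages with no adjustment for time at risk, in a study with open-ended, subject-specific follow-up and long-term safety as its sole objective. They cannot be read as long-term risk in the pooled column or the regional ones. That conclusion rests on the design text alone.

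Confounding of the regional columns is conditional: none if exposure is alike, and about 11 to 16 points at 12 versus 24 months' median exposure. That range assumes exponential treatment times and a common constant rate of 12 to 120 per 100 patient-years. Which case applies is not known from the documents.

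A separate documentary defect is certain: the SAP omits the protocol's timing and time-to-event summaries while stating that no changes are expected. The change is worth making before the tables are produced. It does not call the conduct of the study into question.

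**What to change.** 1. **SAP 6.5.2.** Beside n (%), add the exposure-adjusted incidence rate: subjects with a first event divided by person-years from first dose to the first event or the end of the TEAE window, per 100 patient-years, with an exact Poisson 95% CI. Apply it to the overview rows (any TEAE, Grade 3 or higher, serious, fatal, treatment-related, leading to discontinuation) and to the most frequent preferred terms, overall and by region. Counting first events only avoids the need for a rule on grade changes.
2. **Time at risk.** Show it for the same columns, so that a reader can see whether exposure differs between China and Rest of World.
3. **Interpretation.** Present the rates descriptively, with a note that the regional columns mix treatment cohorts. Do not tell readers to take column differences from the rates.
4. **Consistency.** Restore the summaries planned in protocol 9.7.1.6 and 9.7.1.8, or declare and justify their removal in SAP section 8.

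**Cost.** SAP wording, some programming and slightly wider tables. No new data collection is needed: study drug administration is recorded, time on treatment is already derived, and AE dates are already used, with imputation where partial, to assign treatment-emergent status. The drawbacks are the constant-hazard reading of a rate and wide intervals at about 50 subjects, which the reader should see in any case.
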